**FORM: Application for Human Research**

NUMBER	FORM DATE	PAGE
F200	02/2014	22 of 39

- f. **Code Substitution.** This test assesses visual search, sustained attention, and working memory by asking the user to compare a displayed digit-symbol pair with a set of defined digit-symbol pairs (the key). The user presses designated buttons to indicate whether the pair in question represents a correct or incorrect mapping. In the Learning phase (simultaneous presentation mode), the defined pairs are presented on the screen simultaneously with the digit-symbol pair in question. In the Immediate Memory test that follows the learning phase, the comparison stimuli are presented individually without the key. In the Delayed Memory test presented later in the battery, the comparison stimuli are again presented individually without the key.
- g. **Matching to Sample.** This test assesses spatial processing and visuo-spatial working memory. The user views a pattern produced by eight shaded cells in a 4x4 sample grid. The sample is then removed and two comparison patterns are displayed side by side. One grid is identical to the sample grid and the other grid differs by one shaded cell. The user is instructed to press a designated button to select the grid that matches the sample.
- h. **Mathematical Processing.** This test assesses basic computational skills, concentration, and working memory. An arithmetic problem involving three single-digit numbers and two operators is displayed (e.g., "5 - 2 + 3 ="). The user presses buttons to indicate whether the answer to the problem is less than five or greater than five.

2. **Repeatable Battery for the Assessment of Neuropsychological Status (RBANS)**. The RBANS is a brief battery of well-normed neuropsychological tests. The test is commonly used for assessing individuals with traumatic brain injury. The RBANS has two alternate forms to permit repeated testing. Subtests include: List Learning, Story Memory, Figure Copy, Line Orientation, Digit Span, Coding, Picture Naming, Semantic Fluency, List Recall, List Recognition, Story Recall, and Figure Recall. The test provides several index scores, including: Total Score, Immediate Memory, Visuospatial/Constructional, Language, Attention, and Delayed Memory. Alternate forms will be counterbalanced across the two groups. This battery will be administered to assess improvement in cognitive abilities in each group (OBJECTIVE 2).
3. **Psychomotor Vigilance Test (PVT)**. To assess simple reaction time/psychomotor speed, a modified 10-minute version of the PVT will be administered on a computer at three time points during the assessment session (approximately every two hours). This version has been shown to provide valid and reliable estimates of psychomotor vigilance during sleep deprivation (Thorne et al., 2005). During this task, participants will monitor a screen and press a response button on the hand held unit each time an "x" target appears. The interstimulus interval will be varied pseudorandomly between presentations to minimize anticipation of the stimulus. Average reaction time from all trials will be scored for each administration. This task will be administered to assess improvement in cognitive abilities in each group (OBJECTIVE 2).
4. **Balloon Analogue Risk Task (BART)**. A computerized task that requires the participant to fill a simulated balloon with air (Lejuez et al., 2002). Points are given for maintaining the flow of air

**FORM: Application for Human Research**

NUMBER	FORM DATE	PAGE
F200	02/2014	23 of 39

and keeping volume of the balloon at as full as possible. The more expanded the balloon gets, the more points are gained. However, all points are lost if the balloon is over-inflated and pops. Thus, the goal is to earn as many points as possible by keeping the balloon inflated safely. The task provides a measure of the willingness to take risks versus “playing it safe.” Administration time is approximately 10 minutes.

5. **Go/No-Go Task (GNG).** This is a computerized measure of response inhibition. Subjects will see two different geometric shapes (circles and squares) that are either large or small. Participants are instructed to press the spacebar (i.e., “go”) to all stimuli types except one (e.g., small circle), which is the “no-go” stimulus. Because the “go” stimuli occur much more frequently than the “no-go” stimuli, participants must inhibit their prepotent response when confronted with the less frequent “no-go” stimuli. Task administration time is approximately 8 minutes.
6. **Tower of London (TOL).** This computerized task measures visuospatial planning and sequencing abilities that depend heavily upon prefrontal cortex executive functions. Participants will use the computer mouse to rearrange a stack of “beads” among three “pegs” of differing size on the computer screen. Ten trials will be given. Administration time is approximately 8 minutes.

## **Neuroimaging Tasks**

### **Diffusion Weighted Imaging (DWI)**

Standard MRI techniques are often insensitive to the axonal injuries common to mTBI. However, a recently developed technique known as Diffusion Weighted Imaging (DWI) has shown particular sensitivity to the types of diffuse white matter damage associated with mTBI. DWI is an MRI technique that measures the directional diffusion of intra- and extracellular water on a cellular scale in an MRI system. This non-invasive measure of water mobility can be used to assess white matter/axonal health through its indirect assessment of cell wall shape, size, and orientation (Mori & Zhang, 2006). DWI is achieved by applying second order calculations to a diffusion weighted MR acquisition. Diffusion weighted scans are MRI images in which the image intensity at a given position has been attenuated according to the amount of microscopic diffusion occurring along a selected direction within that position. This attenuation is controlled by applying sensitizing fields along the selected direction during image acquisition. In a DTI acquisition, several diffusion weighted images are acquired, each with the weighting along one of a selected set of directions. The resulting images are combined to produce an Apparent Diffusion Coefficient (ADC) tensor for each image location. Quantities can be calculated from these ADC components that correspond to physiological characteristics (Alexander, Lee, Lazar, & Field, 2007). Two of these quantities are the Fractional Anisotropy (FA) and the mean diffusivity (MD) which together provide a measure of axonal size and density (Basser, 1995; Budde et al., 2007).

FA and MD have been used for assessment of brain damage following mTBI (Huang et al., 2009; Miles et al., 2008; Rutgers, Fillard et al., 2008). Recent work has suggested that indices of MD are significantly higher in mTBI patients compared to controls, whereas FA indices are typically lower

**FORM: Application for Human Research**

NUMBER	FORM DATE	PAGE
F200	02/2014	24 of 39

(Miles et al., 2008). Moreover, these indices have been shown to correlate with cognitive performance in patients (Miles et al., 2008). FA reductions are most commonly found in the corpus callosum, cingulum, and cerebral lobar white matter (Rutgers, Toulgoat et al., 2008). These changes are often most evident within the first 3 months post injury (Rutgers, Fillard et al., 2008). Here, we hypothesize that mTBI patients undergoing MBLT will show greater improvement (i.e., reduction in FA and MD) during the treatment period than patients receiving SPLT, and that this will correlate with sleep improvement and cognitive/symptom improvement.

Diffusion acquisitions will be taken with two separate 72 direction-weighting scheme. These acquisitions have been found to provide sufficient angular resolution of the composite apparent diffusion coefficient in areas of fiber crossings for possible use in a tractography analysis, while having a short enough acquisition time to be clinically effective. Scans will be acquired on a 3T MRI system (Siemens Skyra Syngo) using a standard single shot, spin echo, echo planar acquisition with diffusion weighting gradient pulses.

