**FORM: Application for Human Research**

NUMBER	FORM DATE	PAGE
F200	02/2014	9 of 39

laboratory and provide excellent resolution for evaluating functional changes within the target regions of the anterior cingulate gyrus, hippocampus, and prefrontal cortex. Furthermore, the proposed project will directly assess sleep functioning using actigraphy and correlate these changes in sleep with pre-to post-treatment changes in neurocognitive performance and symptom presentation, as well as functional activity changes.

Briefly, individuals who have experienced a mTBI, with or without loss of consciousness, as verified by a medical report, and who complain of sleep disturbance, will undergo an initial psychological assessment, and will be then fitted with an actigraph to wear for the duration of the study in order to measure baseline sleep as well as any changes in sleep patterns. Individuals will then return to complete two comprehensive neurobehavioral assessment and neuroimaging sessions (functional MRI, structural MRI/diffusion tensor imaging; DTI) separated by 6 weeks. During the intervening 6 weeks, participants will be randomly assigned to receive 30 minutes of morning blue light therapy (MBLT) or a sham placebo amber light treatment (SPLT) daily. Sleep quality and quantity will be measured via continuous wrist actigraphy monitors and self-report inventories.

For interested subjects participating in the last phase of recruitment, we will continue collecting wrist actigraphy and self-report data for an additional 6 weeks after completion of the baseline period and light therapy as an optional part of the study. It is hypothesized that MBLT will improve sleep quality and quantity relative to SPLT, and these improvements will be associated with changes in brain function, brain structure, and reduced post-concussion symptom severity at follow-up assessment.

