**I. BIOSTATISTICAL ANALYSIS**

Several global outcomes and their interpretations include:

- 1) “If the effects of MBLT versus SPLT are not different and improvement is observed in both groups”—this would suggest that nonspecific effects (practice, maturation, recovery) occurred but were unrelated to the MBLT treatment. Thus there is no specific benefit to the use of MBLT versus placebo. Based on such an outcome, there would be no recommendation for the use of MBLT for treatment of post-concussive symptoms. Secondary analyses correlating cognitive/symptom improvement with changes in brain structure and function may identify new avenues of research and would still contribute valuable knowledge regarding these relationships.
- 2) “If effects of MBLT versus SPLT are not different and no significant improvement is observed in either group”—this finding is less likely, as continued improvement between the two sessions would be expected due to gradual recovery during the first year and due to practice effects associated with repeated assessment. While such a finding would clearly suggest that there is no specific benefit to the use of MBLT versus placebo, it would raise suspicion that the assessments were invalid or insensitive.
- 3) “If MBLT is better than SPLT”—this is the hypothesized effect. This would support the hypothesis that MBLT is beneficial in the treatment of post-concussive symptoms relative to placebo. Regression analysis between the change in symptoms/neurocognitive function and measures of sleep and mood would identify whether this was due to sleep related changes or whether the changes were due to the mood altering effects of MBLT, or both. Similarly, changes in one condition and not the other will also be examined for their relationship to

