**FORM: Application for Human Research**

NUMBER	FORM DATE	PAGE
F200	02/2014	29 of 39

specific functional and structural changes. Such information will identify target regions that are most affected by MBLT.

4) "If SPLT is better than MBLT"—it would be unexpected to find the placebo group outperforming the MBLT group. However, such a finding would argue against melatonin suppression as the likely candidate for improvement. Such an intriguing finding would necessitate follow on research to identify the causal factors, and if replicated, could in itself lead to new discovery of an alternative treatment approach. Again, secondary correlational analyses with imaging and neurocognitive measures and analysis of the direction of the effects will guide such interpretations.

Per the Department of Defense, all study data will be deposited on the Federal Interagency Traumatic Brain Injury Research Informatics System (FITBIR) database. This is a protected database that provides training approximately monthly.

The National Institutes of Health (NIH), in partnership with the Department of Defense (DoD), is building a secure, centralized informatics system (database) for TBI research. It will serve as a central repository for new data, link to current databases and allow valid comparison of results across studies. The database builds upon an effort to create common data elements for the study of TBI - which are essentially definitions and guidelines about the kinds of data that should be collected, and how to collect these data in clinical studies.

The Federal Interagency Traumatic Brain Injury Research (FITBIR) informatics system is a collaborative effort involving the NIH Institutes and Centers (ICs) and the US Army Medical Research and Material Command (USAMRMC) to develop a biomedical informatics system and data repository for Traumatic Brain Injury (TBI) research.

The FITBIR Informatics System is an extensible, scalable informatics platform for TBI relevant data (medical imaging, clinical assessment, environmental and behavioral history, etc.) and for all data types (text, numeric, image, time series, etc.). FITBIR was developed to share data across the entire TBI research field and to facilitate collaboration between laboratories, as well as interconnectivity with other informatics platforms.

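### The diffusion-imaging hypothesis counts a fall in FA as improvement, although the plan itself describes low FA as the injury finding

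*Combined protocol and SAP*

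**What the plan says.** The Diffusion Weighted Imaging (DWI) section, under Neuroimaging Tasks in Section 3, item 7, introduces the two indices as measures of injury: "FA and MD have been used for assessment of brain damage following mTBI". It then gives the direction of the abnormality for each: "indices of MD are significantly higher in mTBI patients compared to controls, whereas FA indices are typically lower". A little further on it again treats lowered FA as the lesion pattern and says where it occurs: "FA reductions are most commonly found in the corpus callosum, cingulum, and cerebral lobar white matter". It adds that these changes are often clearest in the first 3 months after injury.

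The treatment hypothesis follows. Patients on MBLT are expected to show "greater improvement (i.e., reduction in FA and MD) during the treatment period than patients receiving SPLT", and this is expected to correlate with improvement in sleep and in cognition or symptoms.

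No other part of the document gives a direction for FA or MD. The overall hypothesis at the end of Section 3, item 1 (Background) is non-directional on structure: it expects that better sleep will go with changes, as in "these improvements will be associated with changes in brain function, brain structure, and reduced post-concussion symptom severity at follow-up assessment". Section I, Biostatistical Analysis, refers to structural change only in general terms.

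**The concern.** The parenthesis defines improvement for both indices as a reduction. The plan has just said that injury raises one index and lowers the other, so a reduction in both cannot be recovery in both. A patient whose MD and FA both moved towards control values would meet the definition on MD and fail it on FA.

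The sign will be needed when results are read. Under the hypothesised outcome (MBLT better than sham), Section I says that changes seen in one arm only will be examined against specific functional and structural changes, to find the regions most affected. Where both arms improve equally, it foresees "Secondary analyses correlating cognitive/symptom improvement with changes in brain structure and function". Where sham does better, it says that "secondary correlational analyses with imaging and neurocognitive measures and analysis of the direction of the effects will guide such interpretations". These comparisons call on an account of which structural change is favourable, and for diffusion imaging the only account given as a hypothesis is this parenthesis.

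There is a second risk. With the rationale pointing one way for FA and the hypothesis the other, either FA result could be presented afterwards as the predicted one.

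**Working it through.** The plan gives no effect size, alpha, sidedness or power for the diffusion analyses, so there is no figure to reproduce. The check is a comparison of signs.

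**Inputs, all from the DWI section**
- Injury direction: MD higher than controls, FA typically lower.
- Direction labelled improvement: MD down, FA down.
- That improvement is expected to go with better sleep and with better cognition or symptoms.

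**Rule.** If an index marks injury, movement towards control values has the opposite sign to the injury effect.

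| Index | Injury vs controls | Improvement on the plan's rationale | Improvement as written | Agree? |
|---|---|---|---|---|
| MD | higher | decrease | decrease | yes |
| FA | lower | increase | decrease | no |

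**Consequence for the arm comparison.** Write ΔFA and ΔMD for the change from baseline to post-treatment.
- MD: mean ΔMD(MBLT) − mean ΔMD(SPLT) should be negative on the rationale, and is negative as written.
- FA: mean ΔFA(MBLT) − mean ΔFA(SPLT) should be positive on the rationale, but is negative as written.

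**Consequence for the correlations.** Score sleep and cognitive/symptom change so that a higher value is better.
- ΔMD with either: negative on the rationale, negative as written.
- ΔFA with either: positive on the rationale, negative as written.

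**Extent.** The sentence implies 2 indices × (1 arm difference + 2 correlations) = 6 directional predictions. The 3 for FA are reversed and the 3 for MD are consistent. If cognition and symptoms are counted separately, the figures are 2 × (1 + 3) = 8 and 4. Either way the share is one half, simply because one of two indices is affected. All of it comes from a single parenthesis, so the count shows how far one error reaches; it is not a tally of separate errors.

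**What does not change.** Diffusion imaging is absent from the primary aims listed in Section 3, item 1. No scoring rule or one-sided test is attached to FA. A two-sided p-value for the FA arm difference would be the same under either sign, and the sample size (40 enrolled for 30 complete datasets) does not depend on it.

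**The case against.** The strongest reply is that this is a drafting slip. The sentences before the hypothesis describe FA reductions and related changes, and the parenthesis may be shorthand for a reduction in the FA and MD abnormalities. The correct orientation of both indices is in the same short section, so a careful analyst would not be misled. That is plausible, but it does not rescue the wording: this is the plan's only stated direction for diffusion imaging, it defines improvement in a treatment hypothesis, and it says the opposite of the rationale for FA.

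Other parts of the reply stand as limits:
- The correlation problem is the same error carried forward, since the plan states no signed FA or MD coefficients of its own.
- No rule in Section I uses the FA sign to decide anything. The correlation of cognitive/symptom improvement with brain structure is named under the outcome where the arms do not differ and both improve. The remark on direction of effects belongs to the outcome where sham is better, and does not name FA or MD. The passage for the hypothesised outcome examines structural change without giving a direction.
- The recovery direction is inferred from a patient-control difference. The plan says the changes are often most evident in the first 3 months, while eligibility runs from 4 weeks to 18 months after injury, so some participants may not start with low FA.

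The last point could support a non-directional FA hypothesis, or one justified for later-stage patients. It does not support calling a fall in FA improvement.

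**Conclusion.** The concern holds. The FA half of the diffusion hypothesis contradicts the plan's own description of FA after mTBI; the MD half is consistent. As written, FA moving towards control values would disconfirm the hypothesis and a further fall would be labelled benefit, with the implied FA correlations reversed in step.

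This should be fixed, but its reach is bounded: it affects the labelling and interpretation of one non-primary imaging index and leaves sample size and two-sided test results alone. The size of any FA effect cannot be stated from the document. The conclusion assumes only that recovery means movement towards control values, which is how the section's rationale reads.

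**What to change.** Before the imaging data are analysed, reword the parenthesis in the DWI section to an increase in FA and a reduction in MD. If a reduction in FA really is expected to mean improvement, say so and give the reason, reconciling it with the preceding description of FA after injury.

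Then state the expected correlations with sleep and with cognitive/symptom improvement separately for FA change and MD change, with a sign for each.

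This takes a few words in the protocol. Data collection, procedures and sample size stay as they are.

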**Functional Neuroimaging:**

Blood Oxygen Level Dependent (BOLD) functional magnetic resonance imaging (fMRI) will be collected at UAMC. Functional brain responses during cognitive challenge tasks will permit quantification of brain function changes between the MBLT and SPLT treatment groups (OBJECTIVE 2) and will be correlated with measures of sleep (OBJECTIVE 3). A Trio 3.0 Tesla whole body high-speed imaging device equipped for echo planar imaging (EPI) will be used. Head movement will be restricted using expandable foam cushions. After an automated scout image is acquired and shimming procedures performed to optimize field homogeneity, high resolution 3D MPRAGE sequences will be collected for spatial normalization, positioning the slice prescription, and for subsequent morphometric analysis (see below). Then a T1-weighted and a T2-weighted sequence will be used to gather sets of images to assist in registration of the functional data to the high-resolution anatomical scan. Functional MRI images (blood oxygenation level dependent or BOLD; Kwong et al 1992) will be acquired using a gradient echo T2\*-weighted sequence.

The following paradigms will be administered to volunteers during fMRI scanning. These tasks are visual in nature and will involve back-projection of stimuli onto a screen via a shielded LCD projector and viewed through a mirror mounted on the head coil. The three functional tasks include:

1. Multi-Source Interference Task (MSIT) (Bush & Shin, 2006): This task presents the subject with two alternating conditions. In each trial, three numbers are shown on the screen. For the control condition, subjects simply make a button press using the index, middle, or ring finger of their dominant hand to indicate the spatial location of the “number 1” on the screen (left, middle, or right). For the “interference” condition, subjects again see three numbers on the screen, but two numbers are the same and one is different. The subject must press the key that identifies the numeral (1, 2, or 3) that is different from the other two. The interference task has been shown to reliably activate the anterior cingulate gyrus in previous studies (Bush & Shin, 2006).

